## **2. Experimental design and methods**

**2.1 Study Period:** April 1, 2021 – May 31, 2023

**2.2 Participant Recruitment:** Participants will be recruited from annual health check-ups conducted in Songshan District, Taipei City, and at the Chang Gung Health and Wellness Village. Those enrolled in the main integrated aging study and meeting inclusion criteria will be invited to participate.

**2.3 Inclusion Criteria:**

- 2.3.1 Willingness to sign informed consent
- 2.3.2 Participation in the designated health check-up programs or prior pilot studies
- 2.3.3 Age  $\geq$  60 years (male or female)
- 2.3.4 Able to ambulate independently.
- 2.3.5 Meeting one of the following pre-sarcopenia criteria
  - Grip strength: <28 kg (men), <18 kg (women)
  - Walking speed: <1.0 m/s
  - Muscle mass: <7.0 kg/m^2 (men), <5.7 kg/m^2 (women)

#### **2.4 Exclusion Criteria:**

- 2.4.1 Impaired renal function.
- 2.4.2 Allergy or intolerance to protein supplements.
- 2.4.3 Currently undergoing cancer treatment.
- 2.4.4 Autoimmune diseases.
- 2.4.5 Assessed by a physician as unsuitable to participate.

#### **2.5 Sample Size: 120 participants**

#### **2.6 Measurements, Duration, and Risks Study Procedures:**

- 2.6.1 Participants will undergo nutritional assessment via questionnaire and receive a daily supplement containing 8.5 g whey protein and 1.5 g leucine for 12 weeks.
- 2.6.2 At week 6, participants will return for blood (5 mL) and urine (10 mL) collection and report supplement adherence.
- 2.6.3 At week 12, participants will return for a second round of blood and urine collection, supplement adherence assessment, and sarcopenia-related functional tests (body composition, grip strength, walking speed, and calf circumference).

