# **Nutrition ameliorates the muscle loss of pre-sarcopenia in elderly**

## **1. Background and Research Objectives**

Population aging has become a global concern. Taiwan is projected to enter a “super-aged society” by 2025, with individuals aged 65 and above comprising over 20% of the total population (approximately 4.81 million people). Older adults often suffer from degenerative diseases, leading to progressive disability and diminished quality of life and dignity. Among the physiological declines associated with aging, loss of muscle mass is particularly prominent. When accompanied by reduced muscle strength or physical function, this condition is defined as sarcopenia. Sarcopenia has recently been recognized as a geriatric syndrome and is associated with adverse clinical outcomes such as disability, falls, injuries, hospitalization, and poor recovery from illness. It is considered a major contributor to loss of independence in older adults. Currently, there is no definitive clinical biomarker for sarcopenia. Functional assessments often reflect fatigue and frailty but do not necessarily indicate sarcopenia itself.

This subproject will recruit participants from the main integrated aging study and identify individuals with **pre-sarcopenia** for nutritional intervention. We plan to collect blood and urine samples from 120 participants at two time points: mid-intervention (6 weeks) and post-intervention (12 weeks). Functional assessments related to sarcopenia will be conducted after the intervention. Using metabolomics approaches, we aim to evaluate the effectiveness of nutritional supplementation, identify potential biomarkers for risk sarcopenia, and assess their prognostic value. The findings will contribute to understanding the physiological mechanisms of sarcopenia and support future therapeutic monitoring.

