#### **2.8 Nutritional supplementation**

Participants received sachets containing the nutritional supplement and were instructed to consume two sachets daily over a 12-week intervention period. Each 8 g serving provided 35 kcal, comprising 4.1 g of protein, 1 g of fat, and 2.4 g of carbohydrates. Follow-up assessments were conducted throughout the intervention to monitor adherence. Participants were asked to return both used and unused sachets at each visit, and compliance was defined as consumption of at least 80% of the provided sachets.

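### Do the two descriptions of the daily supplement (8.5 g whey protein plus 1.5 g leucine, against two sachets at 4.1 g protein per serving) contradict each other?

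*Combined protocol and SAP*

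**What the plan says.** The supplement is quantified in two places.

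- Section 2.6.1 (study procedures): participants "receive a daily supplement containing 8.5 g whey protein and 1.5 g leucine for 12 weeks".
- Section 2.8 (nutritional supplementation): participants were "instructed to consume two sachets daily over a 12-week intervention period". On composition: "Each 8 g serving provided 35 kcal, comprising 4.1 g of protein, 1 g of fat, and 2.4 g of carbohydrates". Neither whey nor leucine is named there.

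No sentence connects the two. The document does not say whether 8.5 g is a weight of whey ingredient or of protein, whether the leucine is counted in the 4.1 g, or whether one sachet is one serving.

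Two other statements bear on the consequence. Section 2.8 measures adherence by sachets: "compliance was defined as consumption of at least 80% of the provided sachets". Section 1 states the purpose: "Using metabolomics approaches, we aim to evaluate the effectiveness of nutritional supplementation".

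**The concern.** The supplement is the trial's only intervention, so a reader expects its two descriptions to give the same daily amount. Multiplying out Section 2.8 gives 8.2 g of protein, not 8.5 g, and the leucine, one of only two components named in Section 2.6.1, has no line in Section 2.8.

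If these were two different products or doses, the report could misstate the exposure. Changes in protein- or leucine-related metabolites would then be read against the wrong amount, and nobody could repeat the intervention with confidence.

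**Working it through.** **Inputs.** From Section 2.6.1: 8.5 g whey protein and 1.5 g leucine a day. From Section 2.8: 2 sachets a day; per 8 g serving 35 kcal, 4.1 g protein, 1 g fat, 2.4 g carbohydrate. Assumption: one sachet is one serving.

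**1. Is Section 2.8 consistent with itself?** Energy at 4, 9 and 4 kcal per gram: 4 × 4.1 + 9 × 1 + 4 × 2.4 = 16.4 + 9 + 9.6 = 35.0 kcal. This reproduces the printed figure, so there is no sign of a misprint in the composition.

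**2. Protein against protein.**
- Daily protein from Section 2.8: 2 × 4.1 = 8.2 g. With rounding, 2 × 4.05 = 8.1 g to 2 × 4.15 = 8.3 g.
- Gap to 8.5 g: 8.5 − 8.2 = 0.3 g, and 0.3 / 8.5 = 3.5%.
- With rounding, the gap runs from 8.45 − 8.3 = 0.15 g (1.8%) to 8.55 − 8.1 = 0.45 g (5.3%). Rounding alone does not remove it.

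**3. Does another serving size help?** Two sachets to a serving gives 4.1 g a day; two servings to a sachet gives 4 × 4.1 = 16.4 g. Both lie much further from 8.5 g, so one serving per sachet is the natural reading.

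**4. Ingredient weight against macronutrients.** Suppose 8.5 g is whey ingredient and the 1.5 g leucine is added and counted as protein in Section 2.8.
- Protein from whey: 8.2 − 1.5 = 6.7 g.
- Protein share of the whey: 6.7 / 8.5 = 78.8%. With rounding, (8.1 − 1.55) / 8.55 = 76.6% to (8.3 − 1.45) / 8.45 = 81.1%.
- Mass check. Two servings weigh 16 g. Whey and leucine take 8.5 + 1.5 = 10 g, leaving 6 g of other ingredients. The non-protein part of the whey is 8.5 − 6.7 = 1.8 g. Total non-protein mass is therefore 6 + 1.8 = 7.8 g. Section 2.8 gives 16 − 8.2 = 7.8 g, made up of 2 g fat, 4.8 g carbohydrate and 1.0 g unlisted. The 1.8 g fits within it.

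On this reading the gap is zero.

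**5. Other ways of counting the leucine.** If no separate leucine is counted in the 4.1 g, agreement needs whey that is 8.2 / 8.5 = 96.5% protein. Added leucine lying wholly outside the listed macronutrients does not fit the printed values: only 16 − 8.2 − 2 − 4.8 = 1.0 g a day is left for 1.5 g, although rounding of the 8 g and 1 g figures could make room.

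**6. Does the answer enter any analysis?**
- Compliance: 2 × 84 = 168 sachets over 12 weeks, and the cut-off is 0.8 × 168 = 134.4 sachets. Protein content does not appear in it.
- Scale: the same rule accepts a shortfall of up to 0.2 × 8.2 = 1.64 g of protein a day. The 0.3 g gap is 0.3 / 1.64 = 18% of that.
- Tests: Section 2.10 compares each person before and after supplementation with a paired t-test. The labelled amount is not a term in it, and neither section describes dose levels.

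**The case for a change.** The case for acting is that agreement was obtained by supplying facts the document does not state: that 8.5 g is an ingredient weight, and where the leucine is counted. Under the 79% reading the same words mean 6.7 g of whey-derived protein rather than 8.5 g, which is a wider ambiguity than 0.3 g. A reader of Section 2.8 alone cannot confirm that any leucine was given. Section 2.7.2 also excludes people with known allergies to the supplement's ingredients, so a full ingredient description has practical use.

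This stands as far as it goes. The basis of the 8.5 g is unstated, and consistency has been shown to be possible, not proven. But Section 2.6.1 does state 1.5 g of leucine and nothing contradicts it; the lack of an amino-acid line in a macronutrient list is silence. A larger gap of 10.0 − 8.2 = 1.8 g (18%) arises only by adding whey and leucine and calling the sum protein, and the plan nowhere gives 10 g of protein. As for interpretation, Section 2.10 names no protein- or leucine-related metabolites and plans no dose-response analysis.

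**Conclusion.** This is missing detail about the product, not an error in the plan. The gap is 0.3 g a day (3.5%; 0.15 to 0.45 g with rounding) if 8.5 g is protein mass. It is zero if 8.5 g is ingredient weight at about 79% protein with leucine counted in the 4.1 g. Both figures rest on one sachet being one serving, which the document implies but does not state.

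Whichever reading is true, the same product goes to everyone, the compliance count is the same and the planned comparisons give the same results. The two sections must be reconciled against the product specification when the supplement is described: the basis of the 8.5 g, where the leucine is counted, and servings per sachet. Whoever writes the report can do that in a line. No view is taken here on which amount is right, and no change to design, conduct or analysis follows.

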#### **2.7 Potential Risks:**

- 2.7.1 Blood sampling: Two draws of 5 mL each; minimal risk anticipated.
- 2.7.2 Supplementation: Participants with known allergies to supplement ingredients will be excluded. Any adverse reactions will be reported to the principal investigator immediately.

#### **2.8 Nutritional supplementation**

Participants received sachets containing the nutritional supplement and were instructed to consume two sachets daily over a 12-week intervention period. Each 8 g serving provided 35 kcal, comprising 4.1 g of protein, 1 g of fat, and 2.4 g of carbohydrates. Follow-up assessments were conducted throughout the intervention to monitor adherence. Participants were asked to return both used and unused sachets at each visit, and compliance was defined as consumption of at least 80% of the provided sachets.

## **2.9 Sample collect for NMR spectroscopy analysis and LC-MS spectrometry analysis**

Blood and urine samples were collected from participants following an overnight fast, both before and after the supplementation period. Plasma was separated within 4 hours of collection by centrifugation at  $1,500 \times g$  for 10 minutes. The resulting supernatant was aliquoted into microtubes and stored at  $-80^{\circ}\text{C}$  until analysis.

## **2.10 Statistical Analysis**

Metabolomic data will be processed using Topspin and MassLynx for spectral alignment and peak extraction, followed by multivariate analysis with SIMCA-P, including principal component analysis (PCA). Univariate statistical comparisons will be conducted using t-tests and ANOVA for group-level differences. Paired t-tests will be applied to assess within-subject changes before and after nutritional supplementation. Changes in metabolite concentrations in plasma and urine will be linked to individual health indicators to identify biomarkers associated with healthy aging.

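### Section 2.10 plans group-level t-tests and ANOVA in a one-arm study that declares no groups, leaves the form of the ANOVA open, and gives the week-6 samples no analysis

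*Combined protocol and SAP*

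**What the plan says.** Section 2.10 is the whole statistical plan. It contains two sentences on univariate testing. The first is "Univariate statistical comparisons will be conducted using t-tests and ANOVA for group-level differences", and it names no group, factor, visit or outcome. The second is "Paired t-tests will be applied to assess within-subject changes before and after nutritional supplementation", and it names two time points only loosely.

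The design has one arm. Section 2.6 says "Participants will undergo nutritional assessment via questionnaire and receive a daily supplement containing 8.5 g whey protein and 1.5 g leucine for 12 weeks". Sections 2.3 to 2.8 describe no control, randomisation or allocation. The sample size is given as "2.5 Sample Size: 120 participants", with no derivation.

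On sampling, Section 2.6 says "At week 6, participants will return for blood (5 mL) and urine (10 mL) collection and report supplement adherence" and then "At week 12, participants will return for a second round of blood and urine collection". Section 1 gives the same two times, and Section 2.7 counts two blood draws. Section 2.9 instead describes fasting samples taken before and after supplementation and does not mention week 6. Functional tests are scheduled at week 12 in Section 2.6, not at week 6.

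**The concern.** A test of group differences needs a declared grouping factor, and treatment cannot be that factor here because everyone is treated. Several others could be meant: sex, the three entry criteria in Section 2.3, compliance at 80% of sachets in Section 2.8, or visit. The plan chooses none of them. If it stays open, the factor can be picked after the metabolite data are seen, and a large panel of metabolites gives many chances for a picked factor to look informative.

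If visit is meant, the form of the ANOVA matters, because samples from one person are correlated and an ordinary ANOVA ignores that. If visit is not meant, the only test of change is the two-point paired t-test. Participants then give blood and urine at week 6 with no planned use in that test, and anyone with one missing sample is lost from it.

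**Working it through.** **1. Can the plan's own figure be reproduced?** No. N = 120 comes without alpha, power, effect size, SD, within-person correlation or dropout. The arithmetic below is for scale only.

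**2. Which samples does each reading of the schedule give?**
- Sections 1, 2.6 and 2.7 alone: weeks 6 and 12. There is no sample before supplementation, so the paired before/after metabolite test cannot be done. The only within-person contrast is week 12 versus week 6.
- Section 2.9 alone: before and after. The paired test can be done and no week-6 sample exists to be left out.
- Both combined: before, week 6 and week 12. The paired test can be done and week 6 has no assigned analysis. Three sampling times also do not match the two blood draws in Section 2.7.

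So the schedule has to be settled before any metabolite contrast can be written.

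**3. What if visits were tested as independent samples?** Assumed: n = 120 complete pairs, equal SD at both visits, two-sided alpha 0.05, within-person correlation ρ, normal approximation.
- Paired SE = SD·√(2(1−ρ)/n). Independent-samples SE = SD·√(2/n). Their ratio is 1/√(1−ρ): 1.20 at ρ = 0.3, 1.41 at 0.5, 2.24 at 0.8.
- True size of a nominal 5% test = 2·(1 − Φ(1.96/√(1−ρ))): 1.9% at 0.3, 0.6% at 0.5, 0.03% at 0.7. A simulated one-way ANOVA over three visits that ignores participant gave 1.5%, 0.3% and 0.01%.
- For an effect that pairing detects with 80% power (2.80 paired SEs), power of the unpaired test = Φ(2.80 − 1.96/√(1−ρ)):
  - ρ = 0.3: Φ(2.80 − 2.34) = 68%
  - ρ = 0.5: Φ(2.80 − 2.77) = 51%
  - ρ = 0.7: Φ(2.80 − 3.58) = 22%
  - ρ = 0.8: Φ(2.80 − 4.38) = 6%

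The harm on this reading is missed changes, not false positives.

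**4. Does the scale of the concentrations matter?** Section 2.10 is silent on scale. Simulated lognormal pairs, n = 120, true rise 15%, alpha 0.05:
- Between-person log SD 0.6, log SD of change 0.6, error split equally over the visits: 53% to 55% power raw, 72% on logs.
- Same, with log SD of change 0.4: 88% raw, 97% log.
- Between-person log SD 0.3, log SD of change 0.4: 94% raw, 96% log.
- Between-person log SD 0.6, log SD of change 0.6, all of it added at follow-up: 99.6% raw, 72% log. Here the extra variance itself raises the arithmetic mean, by a factor 1.15 × exp(0.6²/2) = 1.38, so the raw test is answering a different question.

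**5. Would a random participant intercept be enough if three visits are sampled?** Not if correlation decays with time. Take AR(1) with ρ = 0.5. The variances of the three pairwise differences, in units of SD², are 2(1 − 0.5) = 1, again 1, and 2(1 − 0.25) = 1.5 for week 12 versus baseline. A random-intercept model uses about their mean, 1.17. True size for that contrast is about 2·(1 − Φ(1.96·√(1.17/1.5))) = 8.4%. With ρ = 0.7 the variances are 0.6, 0.6 and 1.02, mean 0.74, and the size is 9.5%. An unstructured covariance avoids this.

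**The case against.** The strongest reply is that the plan is silent rather than wrong. A reader might infer that visits will be compared as independent samples, or else that week 6 is wasted. The documents do not support that choice of two. The sentence after the group-level one explicitly pairs the before/after comparison. Group-level differences read at least as naturally as comparisons between people, and the three entry criteria form a three-level factor just as visit might. Repeated-measures ANOVA, or paired tests involving week 6, are not excluded. Between-person comparisons also have a legitimate place, since Sections 1 and 2.10 aim at biomarkers as well as at the effect of the supplement. All of this stands, so the power losses in step 3 of the working cannot be charged to the plan.

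A reader might also infer that failing to specify logs costs power in general. Step 4 shows that the gain varies with the inputs and reverses under another error model.

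The loss from dropping incomplete pairs cannot be sized either, because the documents give no attrition figure.

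The reply does not remove the core. No section supplies the grouping factor, the form of ANOVA is unstated, and nothing assigns an analysis to week 6. These choices determine what is tested, so they are more than missing detail.

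**Conclusion.** The point holds in this form: the groups for the t-tests and ANOVA are undefined in a one-arm study, it is not stated whether the ANOVA is repeated-measures, and the one stated within-person method leaves week 6 without a role and drops participants missing either sample. The week-6 part rests on Sections 1 and 2.6 being right that such samples are taken.

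No loss of power can be attributed to the plan as written. The range of 68% down to 6% in place of 80%, for correlations of 0.3 to 0.8, is conditional on an independent-samples analysis of visits that the plan does not state. The case for logs rests on concentrations being positive and usually right-skewed and on reporting ratios, not on a guaranteed gain in power.

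With complete data, the recommended model gives the same week-12-versus-baseline contrast as a paired t-test on logs. What it adds is a defined use of week 6 and the retention of participants with incomplete samples. This should be changed: the remedy is cheap and uses samples already planned.

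**What to change.** 1. Reconcile Sections 1, 2.6 and 2.7 (collections at weeks 6 and 12, two draws) with Section 2.9 (before and after), so that the sampled visits are clear.
2. For metabolites, replace the group-level sentence with a linear mixed model on log concentration, with visit as a fixed effect and an unstructured within-participant covariance over the visits actually sampled.
3. Name the contrasts: week 12 and week 6 versus baseline if a baseline sample exists, otherwise week 12 versus week 6. Report ratios of geometric means with confidence intervals.
4. Keep the paired before/after t-test for functional outcomes, which are not scheduled at week 6, and state which measurement serves as the before value for each. Keep it for metabolites as a check, where a before sample exists.
5. If between-person comparisons are wanted (sex, entry criterion, adherence), name each in advance and label it exploratory.

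The cost is SAP wording and slightly more analysis work. No new samples are needed for whichever contrasts the reconciled schedule supports; contrasts against baseline require that a baseline sample is in fact taken.

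### Section 2.10 picks biomarkers from many metabolite tests with no multiplicity or false-discovery control, so the expected false share of the candidate list is not bounded

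*Combined protocol and SAP*

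**What the plan says.** Section 1 makes biomarker discovery an aim: the study is to "identify potential biomarkers for risk sarcopenia, and assess their prognostic value". Section 2.10 is the whole statistical plan. After spectral processing and PCA it lists two sets of univariate tests:

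- For comparisons between groups: "Univariate statistical comparisons will be conducted using t-tests and ANOVA for group-level differences"
- For change within participants, in a separate sentence: "Paired t-tests will be applied to assess within-subject changes before and after nutritional supplementation"

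It then gives the biomarker step: "Changes in metabolite concentrations in plasma and urine will be linked to individual health indicators to identify biomarkers associated with healthy aging".

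Neither this section nor any other names the health indicators, the association model, a significance level, a multiplicity or false-discovery procedure, or a rule for declaring a biomarker. Section 2.6.3 lists week-12 measures, "sarcopenia-related functional tests (body composition, grip strength, walking speed, and calf circumference"), which could serve as indicators, but Section 2.10 does not refer to them.

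The sampling times also disagree. Section 1 collects blood and urine at "two time points: mid-intervention (6 weeks) and post-intervention (12 weeks"), and Sections 2.6 and 2.7 agree with that (visits at weeks 6 and 12, two draws). Section 2.9 has samples taken before supplementation as well as after it.

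**The concern.** Two platforms and two biofluids give many features, and each may be tested against more than one indicator. With unadjusted tests, the number of false flags grows with the number of unrelated features, while the number of true flags is limited by how many real associations exist. A reader of the resulting list could not say what part of it to expect to be false. The indicators and the threshold could also be chosen after the data are seen. PCA does not help, because it controls no error rate for individual metabolites.

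The stake is the candidate list, which serves a stated aim. The wording in Section 1 is about potential biomarkers, so the harm does not go beyond that list and whatever is built on it.

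**Working it through.** **Inputs from the documents.** 120 participants (2.5); NMR and LC-MS (2.9); plasma and urine (2.10); four week-12 measures (2.6.3), not designated as indicators. The plan states no error rate, power or feature count, so it has no figure to reproduce.

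**Assumptions, none of them in the documents.** Unadjusted two-sided 0.05; all 120 participants contribute one change value per metabolite; each truly related metabolite correlates with one indicator at r = 0.2 or 0.3; a share π of metabolites is truly related.

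**Step 1, power of one test.** By Fisher's z, power ≈ Φ(√(n−3)·atanh(r) − 1.96).

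- r = 0.3: Φ(10.82 × 0.3095 − 1.96) = Φ(1.39) = 0.917. Simulation from the exact sampling form gives 0.920.
- r = 0.2: Φ(10.82 × 0.2027 − 1.96) = Φ(0.23) = 0.592. Simulation gives 0.596.

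**Step 2, one indicator.** False share = expected false flags / expected flags = 0.05(1−π) / [0.05(1−π) + power·π].

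- π = 1%, r = 0.3: 0.0495 / (0.0495 + 0.0092) = 0.843.
- π = 1%, r = 0.2: 0.0495 / (0.0495 + 0.00596) = 0.893.

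**Step 3, four independent indicators, metabolite listed on any one.** An unrelated metabolite is flagged with probability 1 − 0.95⁴ = 0.1855. A truly related one is flagged with probability 1 − (1−power)·0.95³, which is 0.654 at r = 0.2 and 0.931 at r = 0.3.

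| Truly related | One indicator (r = 0.3 to 0.2) | Four indicators (r = 0.3 to 0.2) |
|---|---|---|
| 1% | 84-89% | 95-97% |
| 5% | 51-61% | 79-84% |
| 10% | 33-43% | 64-72% |
| 30% | 11-16% | 32-40% |
| 50% | 5-8% | 17-22% |

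With indicators correlated 0.5, and features correlated 0.5 in blocks of 10 (simulated), the four-indicator shares are slightly lower: 94-96%, 60-67% and 28-35% at 1%, 10% and 30%.

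**Step 4, with Benjamini-Hochberg at 5%.** Simulated for an assumed 500 features × 4 independent indicators = 2,000 pairs, n = 120, 1-30% truly related. Power per true pair falls from 0.92 to about 0.23-0.63 at r = 0.3, and from 0.60 to 0.02-0.09 at r = 0.2. The simulated false discovery rate is close to 5%.

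That rate is an average that counts an empty list as zero false. The figures in steps 2 and 3 are ratios of expected counts. On that ratio scale the value after adjustment is still about 0.34-0.45 at 1% true and r = 0.2, where about 86% of simulated lists are empty, and about 0.10-0.12 at 1% true and r = 0.3. At r = 0.3 with 5% or more true it is about 0.05. The two measures should not be compared as like for like.

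**Step 5, what change means.** The arithmetic needs only one change value per participant, so it does not depend on which sampling schedule is correct. The interpretation does. If samples exist only at weeks 6 and 12, a before/after metabolite contrast cannot be formed.

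**The case against.** **This is exploratory work.** That stands in part. Strict familywise control is not called for. But Section 2.10 does not label its output as hypothesis-generating and sets no false-discovery rate or replication step.

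**The figures rest on assumptions.** This stands. Across the settings shown the share runs from 5% to 97%, and the plan's word for the biomarker step does not commit to a separate test per feature at 0.05. A reader might infer from the upper figures that most of the list will be false. The documents do not support that: the true share, the effect sizes and the number of indicators are all unknown, and with a large true share most of the list would be right. They support only the statement that the share is uncontrolled.

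**The four week-12 measures are not the plan's indicators.** This stands. Participants come from health check-ups and a larger aging study, so other indicators are possible. The sponsor has to name them.

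**Adjustment does not guarantee the metabolite list.** This stands. The false-discovery claim covers metabolite-indicator pairs. A metabolite declared on any one pair carries a slightly different rate, up to 0.067 in the correlated simulation.

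**The model needs the indicator's baseline.** This stands. Section 1 says "Functional assessments related to sarcopenia will be conducted after the intervention", but eligibility also uses muscle mass, walking speed and grip ("Grip strength: <28 kg (men), <18 kg (women")), so screening values should exist for anyone qualifying on them. Suppose metabolite change correlates 0.3 with indicator change and is unrelated to baseline, and indicator change is independent of baseline with an SD 0.3 times the baseline SD. Its correlation with the week-12 level is then only 0.3 × 0.3 / √(1 + 0.3²) = 0.09.

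**The sampling conflict is a separate defect.** This also stands. It matters here only because it leaves change undefined, and it adds no weight to the error-control point.

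**Conclusion.** The concern holds in this form: a stated aim depends on selecting from many metabolite tests with no error control, so the expected false share of the candidate list is unbounded if unadjusted tests are run. That conclusion comes from the text and needs no assumption about feature counts or effect sizes. Its size cannot be derived from the documents. The illustrative 84-89%, 33-43% and 11-16% (1%, 10% and 30% truly related, one indicator) rest on unadjusted two-sided 0.05, n = 120 and r = 0.2-0.3, and the share rises with several indicators.

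It would go too far to conclude that the list will be mostly false, or that a 5% false-discovery procedure would turn a 95% false list into a 5% one. The first needs inputs that the plan does not give, and the second compares two different measures. The plan should be changed on this point, but the consequence is confined to how far the candidate list can be trusted.

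**What to change.** 1. Reconcile Section 2.9 with Sections 1, 2.6 and 2.7, and state which two samples define change. If there is no pre-supplementation sample, the before/after metabolite paired t-test cannot be run and the contrast must be renamed.

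2. Add to Section 2.10, in words such as these: *The health indicators are listed before analysis [sponsor to list, for example the week-12 measures in 2.6.3]. Each metabolite change is related to each indicator in a model adjusted for age and sex and, where it was measured, for the indicator's baseline value. Benjamini-Hochberg q-values are computed across all metabolite-by-indicator associations, and separately across all features in the paired contrast, at a pre-stated false discovery rate (5% or 10%). Estimates, 95% confidence intervals and q-values are reported for all features. A metabolite is called a candidate biomarker only if it meets the pre-stated q threshold, and candidates are labelled hypothesis-generating.*

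3. State that the false-discovery claim applies to metabolite-indicator pairs. The sex term is suggested because the grip and muscle-mass cut-offs in 2.3.5 differ by sex. The model, the rate and pooling over platform and biofluid are choices. Separate families are acceptable if listed in advance, with the claim limited to them.

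The cost is a few sentences and trivial computation, but also a shorter list and the power loss shown in step 4 of the working, which is severe at r = 0.2. A 10% rate would recover some of it. Reporting every estimate and q-value keeps weak signals visible.
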